## HUMAN SUBJECTS

### ETHICAL CONDUCT OF STUDY

The study will be conducted in accordance with the current guidelines and in accordance with local applicable laws and regulations. All investigators and research personnel will have appropriate human subjects training (i.e., CITI).

### INSTITUTIONAL REVIEW BOARD (IRB)

The IRB will review all appropriate study documentation to safeguard the rights, safety, and well-being of the subjects. The study will only be conducted after IRB approval has been obtained. The protocol, sample ICF, advertisements (if applicable), written information given to the subjects, safety reports, progress reports, and any revisions to these documents will be provided to the IRB by the investigator.

### INFORMED CONSENT

A written or electronic consent form that complies with the policies of local IRB will be utilized. The informed consent form should include the following elements and be in compliance with 21CFR Part 50:

- Title of the protocol
- Name of the investigator
- Study objectives and purpose
- Detailed description of the procedures
- Explanation of the responsibilities of the subject during follow-up interviews
- Any foreseeable risks, anticipated benefits, available alternatives
- An explicit statement of confidentiality
- Non-compensation for participation
- Right to withdraw at any time
- Signature section
- Number to contact the site investigator or a member of the study team with any questions.

Informed Consent will be obtained by the site investigator or designee prior to any research activities. The informed consent form should be the IRB approved version corresponding to the version of the IRB approved protocol, and may occur through an electronic informed consent form approved by Emory IRB. There is no activity required in the screening process that is not typically considered standard of care evaluation for mild traumatic brain injury. A partial-HIPAA waiver will be sought for screening purposes to ensure eligibility prior to being approached for informed consent.

As part of the informed consent process, the patient will be informed of the ability to withdraw participation from the study at any time, without penalty or change in their ongoing healthcare. The study team should discuss any concerns about the study with the patient.

In case of an eConsent process, the patient and/or LAR will be supplied with a link to a HIPPA-approved cloud-based service (RedCAP), in which there will be a copy of the latest version of the IRB-approved consent. The patient and/or LAR will have the ability to sign the consent electronically as an alternative to the written (paper) one.

## SUBJECT CONFIDENTIALITY

All data (case report forms, laboratory specimens, imaging, and other records) kept at the site will be physically and electronically secured to maintain subject confidentiality. Paper records and computers with subject data will be stored in locked office or cabinet. Computer records will always be password protected, and encrypted when possible. The study database is maintained behind a secure firewall, access is password protected for all data entry and access. Clinical information will not be released without written permission of the subject, except as necessary for monitoring by the IRB or other regulatory agencies.

## SUBJECT WITHDRAWAL

In those who wish to discontinue participation, no further data will be collected. Data collected prior to withdrawal will remain in the study database. Those wishing to discontinue participation will also have the informed consent document explained to them, will have any questions answered and will be asked to review and sign an informed withdrawal from the study, however, subjects are not required to complete this document to withdraw. Standard consent procedures will be used. If subjects withdrawal prior to reaching the 30 day outcome visit they will not be counted toward the subject totals in their respective cohort. These subjects will be considered 'incomplete' and coded separately in the electronic database.

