Study Population	Critically ill patients who are admitted to the ICU at Emory University Hospital (EUH) who require mechanical ventilation for at least two days and are awake enough and cooperative to attempt working with the communication device (defined as Richmond Agitation Sedation Scale (RASS) score of -1 to 1).
Enrollment / Duration	Step 1: 60 Patients, approximately 8 months – No Long-Term Outcomes Step 2: 244 Patients, approximately 12 months – With LTO extending to 6 months
Subject Inclusion	
 
• Intensive Care Unit (ICU) Admission
 
• Mechanically ventilated for at least 24 hours
 
• RASS between -1 to 1 at the time of screening (Note: minimal sedation is allowed including low-dose Fentanyl, Dexmedetomidine, Ketamine, Propofol, etc.)
 

Subject Exclusion	
 
• < 18 years of age
 
• Not admitted to the ICU
 
• Inability to follow commands during screening
 
• Known cerebral injury (acute or chronic) in the dominant hemisphere concerning for aphasia on clinical assessment
 
• Significant pre-existing neurologic (i.e., dementia and/or cognitive deficiencies), psychologic, or baseline communication challenges that would confound outcomes assessments (including hearing loss)
 
• Inability to blink or move eyes for any reason
 
• Prisoner or incarceration
 
• Inability or unwillingness to provide informed consent
 
• Unwillingness to be contacted for follow-up
 

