### SUBJECT HOSPITAL DATA

- a) Consent material (study files)
- b) EyeControl measurement session data
- c) Demographic information: age, weight, height, gender, ethnicity
- d) Clinical status on admission (main diagnosis, procedures, or operations done)
- e) CAM-ICU
- f) Lab results, imaging, vitals, and charting during the ICU stay
- g) List of current medications, dose, and route of administration
- h) Medical history
- i) Previous and current head and brain imaging
- j) Previous and current EEG, if available
- k) Outcome measures: modified Rankin scale on discharge, discharge disposition, modified Rankin scale on follow-up clinic visits
- l) Responses of the patient and family members to a structured questionnaire regarding communication and use of the device
- m) Device training success and frequency for proficient utilization
- n) Eye photographs/video to explore possible relation to clinical events

Every study file will contain a fully signed consent form. The study files will be stored in a locked cabinet in a locked office.

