## ELECTRONIC AND PAPER DATA COLLECTION SYSTEMS

REDCap is a secure online database for building and managing research data supported by Emory. All data collection will be input into the electronic data capture system. When subjects are enrolled, they will be sequentially assigned a unique subject code. This unique code will be used in the REDCap database. A centralized subject key that links subject identification with the unique subject code will be maintained in a secured and password protected electronic format.

**Data Handling** – For the duration of the study, the Investigator will maintain complete and accurate documentation including but not limited to medical records, study progress records, laboratory reports, case report forms, signed informed consent forms, correspondence with the IRB and adverse event reports, and information regarding subject discontinuation or completion of the study.

**Source Documentation** – Source documents are defined as original documents, data and records. Investigator will maintain source documents in the subject's medical records and/or subject binders, which confirm the data entered on the electronic case report forms.

**CRF Completion** – Data collection based on source-documented hospital and/or chart reviews will be performed accurately on the eCRFs by research personnel.

**Retention of Study Records** – Study records will be retained at all sites for a minimum of 3 years following the end of subject recruitment and follow-up activities.

**Data Quality** – Routine regulatory monitoring of regulatory compliance will be conducted by the Departmental Clinical Trials Regulatory Specialist.

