## COMPENSATION FOR TIME AND EFFORT

There will be no compensation for time or effort. The study will occur while the patient is in the ICU, and no travel will occur.

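### The withdrawal rule depends on a 30-day visit that the readable documents do not schedule, and no analysis population is named, so it is unclear whether withdrawn patients are analysed

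*Combined protocol and SAP*

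**What the plan says.** The Subject Withdrawal section contains three statements that bear on analysis.

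- The counting rule: "If subjects withdrawal prior to reaching the 30 day outcome visit they will not be counted toward the subject totals in their respective cohort".
- The status of these patients: "These subjects will be considered 'incomplete' and coded separately in the electronic database".
- Their data: "Data collected prior to withdrawal will remain in the study database". Nothing is collected after withdrawal.

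The section does not say whether the retained data are analysed. The Statistical Analysis Plan lists outcomes, covariates, tests, and multiple imputation to be used if missing data are substantial, a term it does not define. It names no analysis population for either step and does not mention withdrawn patients.

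The Schedule of Events has three time points: Day 0, the ICU admission and Day 180. The Synopsis gives Step 1 "No Long-Term Outcomes". The section on compensation adds "The study will occur while the patient is in the ICU, and no travel will occur".

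**The concern.** The cut-off in the withdrawal rule refers to an event that the plan does not define, so the rule cannot be applied as written. No analysis set is stated that would override it. Two analysts could follow these documents faithfully and analyse different patients.

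In Step 2 the comparison is randomised and open-label. If the rule is applied as an exclusion, patients are removed on the basis of something that happens after randomisation. If withdrawal differs by arm and is related to outcome, the comparison is then biased, in a direction that cannot be known beforehand.

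Step 1 has no randomisation and no hypothesis test, but it does report proportions with confidence intervals, including the share of patients able to operate the device. Whether withdrawers are in the denominator changes that figure.

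**Working it through.** **Is there a 30-day visit?** The Schedule of Events shows none. The Step 2 goals give only a telephone assessment 6 months after ICU discharge. Subject Hospital Data lists "modified Rankin scale on follow-up clinic visits", without a date. The Step 2 flow schema cannot be read. So no 30-day visit appears in the readable text, which is not proof that none was intended.

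**How does the cut-off sit against the primary window?** The Synopsis ends the window at 14 days from randomisation, extubation or ICU discharge, whichever is first. The Step 2 design section ends it at 14 days or ICU discharge. Both close it by day 14. Someone who withdraws between day 15 and day 30 therefore has a closed primary window and retained data, yet falls under the not-counted rule.

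**The plan's own sample size.** Inputs from the Sample Size section: difference 2 days, SD 5.2, power 80%, alpha 0.05 (taken as two-sided), minimal Mann-Whitney efficiency. The efficiency value is not printed; 0.864, the standard lower bound, is assumed.

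- n per arm = 2 × (1.960 + 0.842)² × 5.2² / 2² = 106.1, rounded up to 107.
- 107 / 0.864 = 123.8, rounded up to 124 per arm, 248 in total.

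This matches the stated 248, so the section states and contains no allowance for withdrawal.

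**What the two readings would do.** The withdrawal rates here are assumptions.

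- Withdrawers replaced: the number randomised for 248 counted is 248 / (1 − loss), giving 262, 276 and 292 at 5%, 10% and 15%.
- Withdrawers dropped and not replaced, with no bias: noncentral t with effective n = 124 × (1 − loss) × 0.864 per arm gives power of 80.0%, 78.0%, 75.7% and 73.3% at 0%, 5%, 10% and 15%. Starting from the Synopsis total of 244, these are 79.4%, 77.3%, 75.0% and 72.6%.

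**Bias if exclusion is arm-related.** Let w be the share withdrawn in an arm, and gap the mean difference in outcome between stayers and withdrawers, taken as equal in both arms. Dropping withdrawers shifts an arm's mean by w × gap, so bias = (w device − w control) × gap. SE = 5.2 × √(2 / 107.1) = 0.7105 day, where 107.1 = 124 × 0.864. Rates and gaps are assumed:

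| Withdrawn, device v control | Gap (days) | Bias (days) | Share of 2-day target | Two-sided false-positive rate |
|---|---|---|---|---|
| equal | any | 0 | 0% | 5.0% |
| 5% v 2% | 2 | 0.03 × 2 = 0.06 | 3% | 5.1% |
| 10% v 2% | 2 | 0.08 × 2 = 0.16 | 8% | 5.6% |
| 15% v 3% | 4 | 0.12 × 4 = 0.48 | 24% | 10.3% |

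The sign may go either way. The SD is for delirium/coma-free days counted from admission in an observational study, so it only approximates the trial's endpoint.

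**Step 1.** With 60 enrolled and an assumed 10% withdrawn (6 patients), the denominator is 60 or 54. If none of the 6 had succeeded, leaving them out would multiply the reported proportion by 60 / 54 = 1.11.

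**The case against.** The strongest reply is that the clause is about enrolment. It speaks of subject totals and a cohort, not of analysis, and the same section keeps the data. It may also be carried-over text: Informed Consent refers to "standard of care evaluation for mild traumatic brain injury", and the data-handling section of this single-centre protocol says "Study records will be retained at all sites". This stands. A reader might infer that the plan excludes withdrawn patients from the randomised comparison, or that the Step 2 result will be biased. The documents support neither.

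A second reply is that differential withdrawal need not be large. Step 2 patients may use the device as much or as little as they like, so someone who dislikes it can stop wearing it and stay in the study. This also stands. It makes the larger imbalances in the table less likely, and the 10.3% figure needs both a 12-point imbalance and a gap twice the target effect.

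A third reply is that multiple imputation already covers these patients. This does not stand. Imputation is conditional on an undefined amount of missing data, and the plan does not say whose outcomes are imputed.

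Even as a pure accrual rule, the clause has no usable cut-off and leaves the analysis of withdrawers unstated.

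**Conclusion.** The point holds as an ambiguity that should be fixed. The protocol contains an operative counting rule with an undefined trigger, the primary window closes well before any day-30 cut-off, and no analysis population settles who is analysed. If the rule were used as an exclusion, it would discard randomised patients with complete, retained primary outcomes. In Step 1 it could shift the proportion able to operate the device.

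The size and direction of any bias cannot be derived from the documents. The illustrative range is zero to 0.48 day, and it rests wholly on assumed withdrawal rates and outcome gaps. The figures do not show that the sample size is wrong: 248 reproduces, and whether it needs a withdrawal allowance is not settled by this clause.

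**What to change.** Delete the 30-day clause from Subject Withdrawal. If the flow schema does show a day-30 contact, reconcile it with the Schedule of Events; the statements below are needed either way.

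For Step 2, state in the protocol and the analysis plan:

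- All randomised patients count toward enrolment and are analysed in their assigned arm.
- Patients whose primary-outcome window closed before withdrawal contribute their observed outcome.
- Patients who withdraw earlier stay in the analysis set with data up to withdrawal, and their missing outcome is handled by the planned multiple imputation.

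The existing condition that imputation is used only when missing data are substantial should be worded to agree with the last statement.

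For Step 1, state that all enrolled patients are in the denominator.

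A sensitivity analysis that varies the imputed outcomes is optional. The randomisation target should not be raised as part of this change. The sections also describe the primary outcome and the end of its window differently; that conflict should be handled as a separate point.

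The cost is a wording amendment and a little more analysis work. No new data are needed, because pre-withdrawal data are already kept. The downside is reliance on imputation assumptions for early withdrawers, whose later extubation or ICU discharge dates may be unknown because collection stops at withdrawal.

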## SAFETY MONITORING PLAN

No Data and Safety Monitoring Board is necessary for this prospective trial. No untoward medical occurrence is expected due to subjects' participation in this research. Adverse events In the event subjects report medical illness during follow-up phone calls they will be advised to seek medical evaluation (i.e., emergency department, primary care, etc). During the course of this study, if the principal investigator and/or research personnel believe there are unseen clinically relevant adverse events [related to wearing Eye Control Device], all events will be reviewed by the PI with the clinical team and relevant information reported to the local IRB as unanticipated problems. If an immediate safety concern is discovered by the clinical team, this will be addressed immediately by the study PI and may require no further wearing of the headset.

## COMPENSATION FOR TIME AND EFFORT

There will be no compensation for time or effort. The study will occur while the patient is in the ICU, and no travel will occur.

